## General Information

### 1. General Information

#### 1. Project Title

Improvement in Wound Healing with Negative Pressure Wound Therapy for Postoperative Total Hip Arthroplasty

2. **Brief Summary.** Provide a brief non-technical description of the study, which will be used in IRB documentation as a description of the study. Typical summaries are 50-100 words. Please reply to each item below, retaining the subheading labels already in place, so that reviewers can readily identify the content. PLEASE NOTE: THIS SECTION MAY BE EDITED BY THE IRB FOR CLARITY OR LENGTH.

For the target population of adult patients following primary total hip arthroplasty, the randomized clinical trial will be used to evaluate the efficacy of the use of a mobile negative pressure wound therapy(NPWT) device compared to a standard absorptive dressing in the immediate postoperative period. We will apply two dressing types and evaluate the postoperative wounds with a wound scoring system (ASEPSIS) that incorporates multiple variables of wound infection risk.

3. Is this new study similar or related to an application already approved by a UNC-Chapel Hill IRB? Knowing this will help the IRB in reviewing your new study.

No

### 3. Funding Sources

1. Is this project funded (or proposed to be funded) by a contract or grant from an organization EXTERNAL to UNC-Chapel Hill?

Yes

Funding Source(s) and/or Sponsor(s)

Sponsor Name	UNC Ramses Number	Sponsor Type	Prime Sponsor Name	Prime Sponsor Type	Sponsor/Grant Number	Detail
Kinetic Concepts, Inc. (KCI)	Currently Not Available	Industry		Industry	15-0451	view

2. Is this study funded by UNC-CH (e.g., department funds, internal pilot grants, trust accounts)?

No

3. Is this research classified (e.g. requires governmental security clearance)?

No

4. Is there a master protocol, grant application, or other proposal supporting this submission (check all that apply)?

- Grant Application
- Industry Sponsor Master Protocol
- Student Dissertation or Thesis Proposal
- Investigator Initiated Master Protocol
- Other Study Protocol

### 4. Screening Questions

The following questions will help you determine if your project will require IRB review and approval.

The first question is whether this is RESEARCH 

1. Does your project involve a systematic investigation, including research development, testing and evaluation, which is designed to develop or contribute to generalizable knowledge? PLEASE NOTE: You should only answer yes if your activity meets all the above.

Yes

[The next questions will determine if there are HUMAN SUBJECTS](#) 

2. Will you be obtaining information about a living individual through direct intervention or interaction with that individual? This would include any contact with people using questionnaires/surveys, interviews, focus groups, observations, treatment interventions, etc. PLEASE NOTE: Merely obtaining information FROM an individual does not mean you should answer 'Yes,' unless the information is also ABOUT them.

Yes

3. Will you be obtaining identifiable private information about a living individual collected through means other than direct interaction? This would include data, records or biological specimens that are currently existing or will be collected in the future for purposes other than this proposed research (e.g., medical records, ongoing collection of specimens for a tissue repository).

Yes

*The following questions will help build the remainder of your application.*

4. Will subjects be studied in the Clinical and Translational Research Center (CTRC, previously known as the GCRC) or is the CTRC involved in any other way with the study? (If yes, this application will be reviewed by the CTRC and additional data will be collected.)

No

5. Does this study directly recruit participants through the UNC Health Care clinical settings for cancer patients or does this study have a focus on cancer or a focus on a risk factor for cancer (e.g. increased physical activity to reduce colon cancer incidence) or does this study receive funding from a cancer agency, foundation, or other cancer related group? (If yes, this application may require additional review by the Oncology Protocol Review Committee.)

No

6. Are any personnel, organizations, entities, facilities or locations in addition to UNC-Chapel Hill involved in this research (e.g., is this a multi-site study or does it otherwise involve locations outside UNC-CH, including foreign locations)? You should also click "Yes" if you are requesting reliance on an external IRB, or that UNC's IRB cover another site or individual. [See guidance](#).

No

## Exemptions

### ▪ Request Exemption

Some research involving human subjects may be [eligible for an exemption](#) which would result in fewer application and review requirements. This would not apply in a study that involves drugs or devices, involves greater than minimal risk, or involves medical procedures or deception or minors, except in limited circumstances.

Additional guidance is available at the [OHRE website](#). Exemptions can be confusing; if you have not completed this page before, please [review this table with definitions and examples](#) before you begin.

1. Would you like your application evaluated for a possible exemption?

No

## Part A. Questions Common to All Studies

### ▪ A.1. Background and Rationale

A.1.1. Provide a summary of the background and rationale for this study (i.e., why is the study needed?). If a complete background and literature review are in an accompanying grant application or other type of proposal, only provide a brief summary here. If there is no proposal, provide a more extensive background and literature review, including references.

Periprosthetic joint infections are a devastating complication due to their difficulty in treating, burden on the system, and patient morbidity and occurs in approximately 0.5% to 3% of primary total joint arthroplasties.[1–4] Revision total knee has both a detrimental physical and economic burden. Patients require treatment with intravenous antibiotics, multiple surgeries, and prolonged hospital courses. The clinical outcome of revision surgery for infection is also worse compared to other reasons for revision.[5] Periprosthetic infections also place a significant burden on hospitals. Increased blood loss, complications, and operative time lead to higher total hospital costs, longer hospital stays and increased outpatient visits. Revision arthroplasty compared to aseptic revision can cost more than \$60,000 more.[4] The cost of revision total joint arthroplasty is expected to be 1.6 billion in 2020.[6]

Periprosthetic infections can be related to a number of different factors both patient and environmental. Patient factors such as rheumatologic disease and obesity increase the risk of infection.[7–9] There is also evidence that surgical factors can increase a patient's risk. Time in the operating room, increased traffic, and protective clothing can also impact a patient's chance of developing a SSI.[10,11] Postoperative wound dressings have also been targeted as a means for reducing infection risk. Standard dressings generally consist of sterile absorptive dressings over the incision. Changes in dressing duration and type have yielded varying results. Recently, the use of Negative Pressure Wound Therapy (NPWT) has been investigated for the use on postoperative clean wounds.[12–18]

NPWT was developed for the use on open wounds. Granulated foam is placed over the wound and negative pressure through the form of suction is applied. The benefit of this therapy is hypothesized to be multifactorial including increasing blood flow, reduction of hematoma, and sequestering of the wound from the outside environment.[19] NPWT has been used successfully in orthopaedics for traumatic wounds and surgical infections. Due to this success the use of NPWT expanded to postoperative infection prevention. A study by Pachowsky et al. used a NPWT device specifically designed for closed wounds to reduce post operative seromas in total hip arthroplasty.[15] The study used the PREVENA™ system from Kinetic Concepts Inc. (KCI) to reduce seromas in size from 5.08ml to 1.97ml after 10 days post-op. The PREVENA™ system is a mobile wound therapy device that operates through a battery-powered pack allowing the patient greater mobility than a standard suction device. [20]

Given the success of the system in reducing postoperative seromas it may help reduce the risk of postoperative surgical site infection (SSI). Evaluation of SSI in total joint arthroplasty is difficult given the low incidence in primary arthroplasty. Comparing the incidence of infection with two dressings is difficult given the large amount of patients required to obtain a statistically significant difference. Therefore, evaluating a method that can reduce risk factors for infection such as seroma development becomes more achievable. However, the risk of SSI postoperatively is not limited to the development of a seroma. Wound dehiscence and drainage are also indicated as potential risk factors for SSI. Patients that develop drainage, erythema or dehiscence require increased concern for infection and can lead to additional procedures including diagnostic aspirations, scar revision and irrigation and debridement. The previous study's evaluation of seroma did not evaluate many of these factors that can lead to SSI.

Another method of evaluating wounds for SSI risk that incorporates multiple wound healing factors such as erythema, drainage, and dehiscence is the ASEPSIS ( Additional treatment, presence of Serous discharge, Erythema, Purulent exudate, Separation of the deep tissue, Isolation of bacteria, and duration of inpatient Stay) wound scoring system.[21] Originally developed and validated for cardiac surgery sternal wounds, ASEPSIS evaluates the wound for the severity of multiple factors linked with surgical site infection.[22–25] This includes dehiscence, exudate/discharge, and erythema. The scoring system also includes secondary procedures that increase patient morbidity such as surgical procedures and the use of antibiotics. The higher the score, the more likely a surgical site infection will be present. This score will give us a more diverse picture of postoperative wound healing and the influence of NPWT.

### ASEPSIS Scoring System

Characteristic	Percent of Wound Affected					
	0	<20	20-39	40-59	60-79	>80
Serous Exudate	0	1	2	3	4	5
Erythema	0	1	2	3	4	5
Purulent Exudate	0	2	4	6	8	10
Separation of Deep Tissue	0	2	4	6	8	10

Additional Points for: Antibiotic Treatment- 10 Local Debridement- 5 OR Debridement- 10 Isolation of Bacteria- 10 Hospitalization >14 days- 10

The scoring system is designed to translate the appearance of the wound with the clinical appearance. Stricter methods of evaluating wounds (such as evaluating for pus) can miss lesser degrees of infection. This score helps to overcome the challenge of a small incidence of grossly infected wounds by identifying the skin changes associated with infection. Wilson et al. identified an ASPESIS score >20 as being more sensitive and as specific as the presence of pus as an indicator of changes in management resulting from infection [24]. The scoring method has also been shown to be both repeatable (intraobserver reliability of 0.96 and coefficient of repeatability of 4.1) and validated against the CDC criteria in general surgery procedures.[22,25]

#### A.1.2. State the research question(s) (i.e., specific study aims and/or hypotheses).

Does the use of a negative pressure wound therapy system improve wound healing as measured by the ASEPSIS score on postoperative primary total hip arthroplasty patients?

Aim 1. Wound Healing. Compare the two dressings in terms of their ASEPSIS wound healing score after 1 week, 2 weeks and 6 weeks post operatively. The anticipated result is that the NPWT will show improved wound healing.

Aim 2. Secondary Procedures. Compare the two dressings in terms of requirements for secondary events such as aspirations, ER visits for wound concerns, and return to the operating room. The anticipated result is that the NPWT will decrease secondary events.

Aim 3. Safety. Compare the two dressings in terms of frequencies of adverse events. The anticipated result is that the research subjects will experience no significant difference in the number of adverse events relative to the standard regimen.

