### A.4. Study design, methods and procedures

*Your response to the next question will help determine what further questions you will be asked in the following sections.*

A.4.1. Will you be using any **methods or procedures commonly used in biomedical or clinical research** (this would include but not be limited to drawing blood, performing lab tests or biological monitoring, conducting physical exams, administering drugs, or conducting a clinical trial)?

Yes

A.4.2. Describe the study design. List and describe study procedures, including a sequential description of what subjects will be asked to do, when relevant.

Patients will undergo primary total hip arthroplasty with identical preoperative and intraoperative care. The patients will then be divided into two groups depending on their randomization. All postoperative care will remain the same other than the choice of dressing placed postoperatively. They will remain in the hospital for 2-3 days(standard of care). On Post op day two they will receive a dressing change regardless of their regimen(standard of care). Patients will be discharged home or to a skilled nursing facility with instructions regarding wound care in both regimens. They will receive assistance through home health or through their nursing facility in case of dressing issues although there will be no intended dressing change or other alteration of the dressing until their next followup. Instructions for the study will be included in the discharge instructions and

include a phone number for questions, these instructions are provided on another attachment. The patients will return to clinic on Post op day seven. They will have their wound evaluated and the dressing changed with their wound evaluated for ASEPSIS (the details of the scoring system and references are provided in the background). They will return on post op day 14 and again have their wound evaluated. Their staples will also be removed. They will be monitored until their 6 week visit for any complications.

Standard Regimen.

Post Op Dressing	Staples over surgical incision, Adaptic® dressing, Abdominal Dressing pad, Tape
POD2	All dressings removed, staples remain in place, Island dressing placed
1 Week Post Op	Island dressing removed and new sterile island dressing placed *Wound evaluated
2 Weeks Post Op	Island dressing removed and staples removed, no dressing placed *Wound evaluated

Experimental Regimen.

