Post Op Dressing	Staples over surgical incision, NPWT dressing
POD2	Dressing removed, staples remain in place, New sterile NPWT dressing placed

	NPWT dressing removed and sterile island dressing placed
1 Week Post Op	*Wound evaluated
2 Weeks Post Op	Island dressing removed and staples removed, no dressing placed *Wound evaluated

The evaluations to be recorded, and the occasions of evaluation, are detailed in **Table 1a** and **Table 1b**.

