**Table 1b. Measurements Recorded: Treatment and Response Data**

Measurement	1 Week Post op	2 Weeks Post op
Serous Exudate	X	X
Erythema	X	X
Purulent Exudate	X	X

Separation of Deep Tissue	X	X
Antibiotic Treatment	X	X
Local Debridement	X	X
Operative Debridement	X	X
Positive Bacterial Culture	X	X
Hospitalization >14 days	X	X
Adverse Events	X	X

A.4.3. If subjects are assigned or randomized to study "arms" or groups, describe how they are assigned.

- *Describe the methods of computing the randomization schedule (if any) and maintaining blinding (if any).*
- *Who will perform these computations?*
- *How will you verify each subject's eligibility prior to randomization?*

Treatment regimen will be assigned to research subjects by a randomization procedure performed through the REDCap software. An independent member of the TraCS team and software manager ([name]) will assist in developing the randomization. Prior to surgery the research team will be informed of the selected treatment group and provide the dressing to the surgeon intraoperatively. Subsequently, the assigned treatment may be adaptively modified in some ways to protect the well-being of the subject. Such modifications may create a departure from protocol.

Randomization procedure. The randomization procedure will assign the research subjects (i.e., the experimental units) to the two treatment regimens in a 1:1 ratio. De

Blinding. This will be an unblinded, open-label study. Both patients and their respective care teams will be aware of the treatment regimen to which each patient has been randomized at the time of enrollment, at the time of informed consent and throughout treatment.

Protocol Departures. Although early termination of the subject's dressing is not anticipated, it is possible that some research subjects will require modifications of their dressing or care that constitute departure from the assigned treatment regimen. A case by case decision will be made to either continue the protocol or to drop the patient from the study and make needed changes. Protocol departures will be carefully documented. Subjects whose medical care departs from the protocol will continue to be evaluated per protocol and the resulting data will be recorded in the database for use in intent-to-treat (ITT) statistical analyses.

A.4.4. Describe any follow up procedures.

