### A.8. Data analysis

#### A.8.1. Summarize the statistical analysis strategy for each specific aim.

Our primary goal is to test the difference between two independent groups at one week post op. Our feasible total sample size is 80 subjects. The progression of the ASEPSIS score over the six week post op recovery period will not be rectilinear. All patients are expected to be infection free with very low ASEPSIS scores immediately following the operation and are likely to be fully healed at six weeks. Attempting to model the timecourse of the ASEPSIS score with splines or multiple dummy variables and including all potential covariates would require considerable degrees of freedom and model tweaking based on intermediate assessments of model fit. Such a model would likely be too saturated to yield meaningfully narrow standard errors and holds considerable danger for overfitting. This modeling process does have some value for exploratory purposes, and we will employ it as such, but it will not be appropriate for confirmatory hypothesis testing. Instead, we note that the timepoint when differences in wound healing are most pronounced is after one week. Because subjects will be randomized to the two arms, we can consider the relevant population to be balanced on their covariates. The null hypothesis is simply that the treatments do not differ in ASEPSIS score at one week post op. Thus, we have a two independent groups t-test as a valid test

of our a-priori hypothesis.

A biostatistician ([name], NC TRACS) has been recruited and will provide the statistical computations and interpretive analyses required for the exploratory model-based analyses of the data. Estimates of effect magnitude, confidence intervals and sensitivity analyses will augment the exploratory modeling that will be conducted.

**A.8.2. What are the practical objectives of the study? Examples: pilot study to obtain data for a grant proposal, train junior investigators, create a registry, develop new assay methods, pilot-test procedures, evaluate feasibility, generate hypotheses, estimate parameters, test hypotheses.**

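### Aim 1 promises a 6-week ASEPSIS comparison, but wound scoring is scheduled only at weeks 1 and 2, and the event record in Table 1b also stops at week 2

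*Combined protocol and SAP*

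**What the plan says.** **The aim.** Section A.1.2, Aim 1: "Compare the two dressings in terms of their ASEPSIS wound healing score after 1 week, 2 weeks and 6 weeks post operatively". Aim 2 adds secondary events, with aspirations, ER visits for wound concerns and return to the operating room as examples. Aim 3 compares adverse events.

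**The analysis.** Section A.8.1 places the confirmatory test at week 1 alone. It also treats the score as having a six-week course: "The progression of the ASEPSIS score over the six week post op recovery period will not be rectilinear". It mentions splines or multiple dummy variables for that course and says of such modelling: "This modeling process does have some value for exploratory purposes, and we will employ it as such". It expects patients to be "likely to be fully healed at six weeks".

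**The schedule.** Section A.4.2 scores the wound with ASEPSIS on day 7. For the next visit it says: "They will return on post op day 14 and again have their wound evaluated". After that it says only: "They will be monitored until their 6 week visit for any complications". The tables are introduced with "The evaluations to be recorded, and the occasions of evaluation, are detailed in" Tables 1a and 1b. The table headed "Table 1b. Measurements Recorded: Treatment and Response Data" has two time columns, 1 week and 2 weeks.

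**General wording elsewhere.** Section A.4.4 says wounds are evaluated during follow-up, and section B.3.2 refers to wound checks at clinic visits. Neither names week 6 or a score. Section A.8.4 commits to recording secondary events for exploratory use, and section A.8.5 allows study data to be taken from the medical record.

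**The concern.** An aim names three time points and the schedule that should supply them names two. Staff working from Table 1b would take no ASEPSIS score at the 6-week visit, and a wound appearance that was not scored at the time cannot be recovered later. The week-6 part of Aim 1 would then be unreportable, and the exploratory six-week model would have nothing to fit beyond about day 14.

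The same table governs the event data. Its last column is week 2, while complication monitoring continues to week 6. Events in Aims 2 and 3 that arise in the later weeks have no defined field or collection point, so their capture could vary between subjects. In an open-label trial, it could also vary between arms.

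**Working it through.** **1. The plan's own figure.** Section A.8.4 gives 80% power for a 0.63 SD difference with 40 v 40 at week 1. The documents state no alpha, so I assume 0.05 two-sided. The noncentrality is 0.63 × √(40/2) = 2.817. Power is Φ(2.817 − 1.960) = Φ(0.857) = 80.4% by the normal approximation, and 79.5% by the exact noncentral t. The figure is reproduced. It uses week-1 scores only, so nothing below changes it.

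**2. Time points set side by side.**

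| Source | Week 1 | Week 2 | Week 6 |
|---|---|---|---|
| Aim 1 (A.1.2) | ASEPSIS compared | ASEPSIS compared | ASEPSIS compared |
| Visit narrative (A.4.2) | ASEPSIS scored | wound evaluated | complications only |
| Standard regimen table | wound evaluated | wound evaluated | no row |
| Experimental regimen table | wound evaluated | wound evaluated | no row |
| Table 1b, nine ASEPSIS items | marked | marked | no column |
| Table 1b, Adverse Events | marked | marked | no column |
| Monitoring plan (A.7.1) | clinic return, about day 7 | clinic return, about day 14 | not mentioned |

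Three occasions are named in the aim and two are scheduled. The four places that describe wound evaluation by visit (narrative, two regimen tables, Table 1b) agree with one another. A column lost in the PDF reading is therefore not a plausible explanation.

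**3. What the exploratory model could do.** Take week 1 as reference, T for treatment arm, and W2 and W6 as visit dummies:

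E(Y) = β0 + β1·T + γ2·W2 + γ6·W6 + δ2·T·W2 + δ6·T·W6

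The week-6 arm difference is β1 + δ6. With no week-6 scores, the columns W6 and T·W6 are zero for every observation. γ6 and δ6 are then not identified, and the difference cannot be estimated. A spline would return a value at day 42, but that value would come from the assumed shape beyond about day 14. The plan specifies neither knots nor form, so I attach no standard error to it.

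**4. What scoring at week 6 would give.** With 40 complete subjects per arm, the standard error of the difference is √(1/40 + 1/40) = 0.224 SD of the week-6 score, the same precision as at week 1.

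**5. Event record.** Monitoring runs to week 6 (6 × 7 = 42 days) and the last Table 1b column is at day 14. Days without a column: 42 − 14 = 28, and 28/42 = 67%. Of the three example events in Aim 2, aspirations and ER visits for wound concerns have no row. Return to the operating room is covered only in part, by Operative Debridement.

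**The case against.** The strongest reply is that a week-6 wound check is plainly intended and the table merely omits it. A 6-week visit exists, section A.4.4 has wounds evaluated during follow-up, and section B.3 describes six contacts over 8 weeks that involve wound checks. The intention is plausible, and a reader should not infer that week-6 scores will certainly be absent. But none of these statements schedules an ASEPSIS score or names week 6, and they do not override the table that is said to define the occasions.

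A reader might also infer that capture of Aim 2 events is unplanned. The documents do not support that. Section A.8.4 commits to recording them, section A.8.5 provides for medical-record review, and section A.7.1 has a list for identifying readmissions and passes patients' reported problems to the research team. What stands is narrower: these events are not defined as variables in Table 1b, and no collection point is set after week 2. The ER admission date and time in section A.8.5 is a tracking-file identifier, not a wound outcome.

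Finally, the stakes are modest. Week 1 is the only confirmatory time point, the time-course model is exploratory, secondary events are not powered, and little difference between arms is expected in wounds that should have healed by six weeks. All of that stands. It limits the importance of the point but does not remove the contradiction.

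**Conclusion.** The inconsistency is real and should be corrected. If the schedule is followed as written, one of three Aim 1 comparisons has no data and a dummy-variable model cannot supply it. About 28 of 42 days of complication monitoring lie beyond the last Table 1b column, and two of the three Aim 2 example events have no row. The contradiction itself rests on the text alone. The only assumption is the two-sided 0.05 alpha used to reproduce the power.

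It would be wrong to read this as a flaw in the primary analysis. The week-1 t-test, the 40 v 40 target and the 80% power do not depend on any later visit. The loss falls on secondary and exploratory results. There is also a tension between section A.7.3 (withdrawal after certain complications) and section A.4.3 (continued evaluation after protocol departures). That is a separate matter and is not needed for this conclusion.

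**What to change.** Choose one of two options for the score.

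1. **Score at week 6.** Add a 6-week column to Table 1b for the nine ASEPSIS items, and a week-6 wound evaluation to both regimen tables, using the visit that already exists. Section B.3.2 caps research time at 10 minutes per visit, so the most it can cost is 80 × 10 = 800 minutes (13.3 hours), or 90 × 10 = 900 minutes (15 hours) if all 90 recruits are scored. The drawback is that little contrast is expected by then.
2. **Drop week 6.** Delete it from Aim 1 and limit the exploratory model in section A.8.1 to weeks 1 and 2. The cost is that the trial can say nothing about ASEPSIS-measured healing after week 2.

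Under either option, extend the existing Adverse Events and Operative Debridement rows to the 6-week visit. Add rows for aspiration, ER visit for a wound concern and return to the operating room, collected through that visit in the same way in both arms. This needs changes to protocol and case report form wording and no new visit. It should be settled before data collection, because missed week-6 wound scores cannot be reconstructed.
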